#### **4.2.7. Termination Visit and Early Discontinuation from Long-Term Follow-up Visits**

If a subject prematurely discontinues from the long-term follow-up portion of the study, all reasonable measures will be taken to perform an Early Discontinuation Visit. This visit should include all procedures listed in the Follow Up and updating of subject contact information.

#### **4.2.8. Unscheduled Visit**

Unscheduled visits will be performed upon the investigator's discretion, upon Sponsor request to redo tests with unusual results, or to complete missing results. These visits may also occur upon subject's parent or guardian request. Unscheduled visits will include any study procedure deemed necessary.

During the long term follow-up period after the intervention period and Week 28 visit, this patient population is expected to continue routine Standard of Care visits that may be conducted at approximately three month intervals. If these routine Standard of Care visits are conducted the following data will be collected: body weight, body length, head circumference, parenteral nutrition intake, enteral nutrition intake, re-hospitalizations and adverse events. These data will be entered into the eCRF as Unscheduled Visits. If a routine Standard of Care visit is not conducted or complete data are not collected as part of these visits, these will not be considered missing data. These data will include neurodevelopmental Bayley's score cognitive, language and motor domains at 2Y corrected age.

### **5. SAFETY CONSIDERATIONS AND GUIDANCE FOR INVESTIGATORS**

Adherence to protocol monitoring procedures along with the following safety guidance will aid and promote subject safety.

## 5.1. SAFETY MEASUREMENTS

Nutrinia has performed four trials, three in preterm infants and one in SBS infants, with oral administration of insulin. In these trials no treatment-related adverse event has been reported and no systemic absorption of insulin was detected. The NTRA-9620 formulation has been extensively studied in two clinical studies with pre-term infants (26-33 week gestational age) and in one clinical study with term infants (34-42 week gestational age). [Table 1](#) summarizes the non-drug related AEs and SAEs observed in the previous clinical trials.

**Table 1: Adverse Events Observed in Previous Nutrinia Clinical Studies of Oral Insulin in Premature Infants**

According to the study investigator, none of the recorded adverse events was related to the investigational product or trial.

### Phase I Efficacy Trial (n = 8)

Adverse Events	No. of subjects with an event (n = 8)
Green gastric residue + residue of 20-50% of the prior meal, 3 meals in a row	1
Bradycardia	1
Hypertension	1
Apnea	1

### Phase I Safety Trial (n = 11)

Adverse Events	No. of subjects with an event (n = 11)
Seborrhea dermatitis	1
Rhinitis	3
Rosseolla infantum	1
Upper respiratory tract infection	1
Cough	1
Soft stool	1
Conjunctivitis	1
Viral infection	2
Mild stridor	1
Otitis media mild	1
Fine macular rash on face and abdomen	1

Adverse Events	No. of subjects with an event (n = 11)
Fever	1
Viral rash	1

### Phase II Efficacy Trial (n = 33)

Adverse Events	No. of Subjects affected	Number of AE defined as Serious Adverse Events (SAE)
Coffee ground	1	0
Supraventricular tachycardia	1	0
Gastro enteritis	2	1
Hernia Inguinal	4	0
Low hemoglobin	1	0
Sepsis due to staphylococcus epidermidis	1	0
Sepsis gram positive colli	1	0
Sepsis	4	2
Acute otitis media	1	0
Upper respiratory tract infection	2	0
Respiratory distress	1	0
Rt. Upper Lobe pneumonia	1	1
Neutropenia	1	0
Hypothyroidism	2	1
Gastroesophageal reflux	1	1
Diaper dermatitis	1	0
Skin irritation	1	0
Ulceration of strawberry hemangioma	1	0
Apnea	2	1
Fever	1	1
Mild conjunctivitis	1	0

## **5.2. PREMATURE DISCONTINUATION FROM STUDY MEDICATION**

Subjects will be discontinued from the study medication after evaluation by the investigator and sponsor's medical monitor in any of the following cases:

- Any CTCAE Grade 3 or 4 adverse event (see Section 7) that the investigator considers related to study medication and not attributable to the underlying disease or considered common events listed in [Appendix C](#).
- Systemic hypersensitivity reaction related to study medication.
- Non-compliance of the subject's parent(s) or legal guardian(s) with study procedures
- Other reasons regarded as warranting subject's discontinuation from study medication.
- Premature study termination as described in Section 5.3.

Parent(s) or legal guardian(s) who voluntarily have their child discontinue the study medication will be questioned to determine whether an AE contributed to the decision to discontinue study medication.

Subjects who are withdrawn from treatment because of an adverse event will be followed and treated by the investigator until the abnormal parameter/condition or symptom has resolved or stabilized or the investigator deems further observations or examinations no longer required as medically indicated.

The investigator will make reasonable attempts to provide a reason for a subject's being withdrawn from study medication. The reason for the subject's withdrawal from study medication will be described in the subject's source documents and CRF

Subjects who prematurely discontinue will have an Early Discontinuation for Study Medication Visit as described in Section 4.2.6□ . Subjects who discontinue study medication early should return four (4) weeks after study medication discontinuation to receive follow-up visits.

## **5.3. PREMATURE DISCONTINUATION FROM STUDY**

Participation in the study is strictly voluntary. In accordance with the current revision of the Declaration of Helsinki, parent(s) or legal guardian(s) of subjects have the right to withdraw their child from the study at any time, for any reason, specified or unspecified, and without prejudice to any future medical care by the physician or the institution. If the parent(s) or legal guardian(s) of subjects choose to withdraw their child, the investigator and the Sponsor must be informed immediately.

The subject will be withdrawn from the study if the parent(s) or legal guardian (s) withdraws consent.

The investigator will make reasonable attempts to provide a reason for withdrawal of subjects from the study. The reason for the subject's withdrawal from the study will be specified in the subject's source documents and CRF. When a parent or guardian asks to withdraw consent, the investigator should confirm that the parent/guardian understands the difference between withdrawal of study medication and withdrawal from the study. If the parent/guardian is willing to withdraw the subject from study medication but remain in the study, then the investigator should follow procedures in Section 4.2.6.

## **5.4. PREMATURE STUDY TERMINATION**

The study subjects are expected to experience many adverse events, including severe adverse events related to premature birth, invasive surgery, their medical/surgical complications or other underlying conditions including but not limited to the short bowel condition. Therefore, all safety concerns potentially leading to study termination will be referred to the Data Safety Monitoring Board (DSMB), which is responsible for a formal assessment of the safety of the study. This Board will propose the appropriate course of action to the Sponsor.

### **Individual Events:**

Any of the following individual events would be referred by the study Medical Monitor to the DSMB chairman for review, who may decide that the events warrant a full DSMB review. The DSMB will review these events unblinded to fully evaluate the potential risk to subjects in this trial. Given this is a blinded trial, the DSMB review is required to consider if the events, both serious and related non-serious events, are occurring more frequently in the active arms and to judge whether there is a meaningful likelihood that these events are drug-related. The DSMB may recommend to the Sponsor to stop the study, or any portion of it, at any time for safety reasons on the basis of their review. Individual events that may trigger a DSMB review based on individual cases:

- Two or more cases of Grade 3 or greater allergic reactions or anaphylaxis, that the investigator deems as possibly related to study medication;
- Any case of autoimmune disease associated with neutralizing antibodies to insulin and where other related causes, such as Type I diabetes, are ruled out;
- Two or more cases of persistent Grade 3 or greater hypoglycemia that is non-responsive to treatment within 72-hours and reoccurs after temporary discontinuation of study medication and re-challenged.
- Two or more subjects who develop liver enzyme increases of greater than 10 times the ULN that is attributed to study medication and the investigator does not consider related to the underlying disease process or administration of parenteral nutrition.

Further, the Medical Monitor will be responsible for review of all reported SAEs in an ongoing manner. Any SAE that is deemed potentially related to study medication, or of particular concern by the Medical Monitor, will also be sent to the DSMB Chairman for review within

15 days. The DSMB Chairmen may decide to bring any individual SAE event that may be related and of concern to the full DSMB for review.

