Possible	A clinical event, including laboratory test abnormality, with a reasonable time sequence to administration of the drug, but which could also be explained by concurrent disease or other drugs or chemicals. Information on drug withdrawal may be lacking or unclear. For the purpose of this protocol, an event that has possible relationship to study medication will be defined as a "Suspected Adverse Drug Reaction".
Probable	A clinical event, including laboratory test abnormality, with a reasonable time sequence to administration of the drug, unlikely to be attributed to concurrent disease or other drugs or chemicals, and which follows a clinically reasonable response on withdrawal. For the purpose of this protocol, an event that has probable relationship to study medication will be defined as an "Adverse Drug Reaction".

In order to classify adverse events and diseases, the sponsor or its designee will assign preferred terms to the original terms entered on the CRF, using the Medical Dictionary for Regulatory Activities (MedDRA).

AEs will be graded on a 5-point scale (mild, moderate, severe, life-threatening, and death) and reported as indicated on the CRF. Intensity of adverse event is defined as follows:

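### The hypoglycemia trigger in Section 5.4 counts a case only if it recurs on re-challenge, so an infant taken off study drug under Section 5.2 for a related Grade 3–4 episode cannot count toward the two cases (minor)

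*Combined protocol and SAP*

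**What the plan says.** Section 5.4 (Individual Events) names four kinds of event that the medical monitor passes to the DSMB chair, who may call a full, unblinded DSMB review. For hypoglycemia there must be at least two persistent cases of Grade 3 or above, and each must be "hypoglycemia that is non-responsive to treatment within 72-hours and reoccurs after temporary discontinuation of study medication and re-challenged".

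The allergy item reads "Two or more cases of Grade 3 or greater allergic reactions or anaphylaxis, that the investigator deems as possibly related to study medication". The liver item begins "Two or more subjects who develop liver enzyme increases of greater than 10 times the ULN that is attributed to study medication" and goes on to exclude cases put down to underlying disease or PN. The autoimmune item needs one case with other causes ruled out.

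Section 5.2 governs the individual infant: "Subjects will be discontinued from the study medication after evaluation by the investigator" and the medical monitor. The first listed reason is "Any CTCAE Grade 3 or 4 adverse event (see Section 7) that the investigator considers related to study medication", provided it is not attributable to underlying disease or to listed common events. What follows is an early discontinuation visit and a return after four weeks. No restart is described.

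In the causality table of Section 7.1.1, the highest category, Probable, requires reasonable timing and an event "unlikely to be attributed to concurrent disease or other drugs or chemicals, and which follows a clinically reasonable response on withdrawal". It does not require re-challenge.

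**The concern.** The hypoglycemia conditions are joined by *and*, so recurrence on re-challenge is necessary for a case to count. Section 5.2 takes an infant off study drug after a single related Grade 3 or 4 event. The two rules pull against each other: the more firmly an episode is blamed on the drug, the more likely the infant is to be stopped, and the less likely the case is to be counted. Hypoglycemia is the obvious systemic risk of insulin, and Section 3.2 says the upper dose is twice the dose tested clinically before, so one would want the count for this event to be complete.

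What is at stake is one referral trigger. It is not a stopping boundary, and it plays no part in the efficacy analysis.

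**Working it through.** There is no stated figure to reproduce. The documents give neither a hypoglycemia rate nor an operating characteristic for the trigger, so the check is one of logic.

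**Step 1. Who can count now.** Take an infant with persistent hypoglycemia of Grade 3 or above that has not responded by 72 hours. Four courses are possible:

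| Course after the episode | Re-challenged? | Counts under the current text? |
|---|---|---|
| Stopped under Section 5.2 for the event | no | no |
| Held, restarted, recurs | yes | yes |
| Held, restarted, no recurrence | yes | no |
| Continued without a hold | no | no |

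The first row is the point at issue.

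**Step 2. Whether the trigger can be met at all.** It can. Section 3.1 allows dose interruptions at the investigator's discretion, none longer than 7 consecutive days. Appendix E lists hypoglycemia as expected with sepsis, TPN weaning, advanced liver disease and prematurity. An episode put down to one of these falls outside the first reason in Section 5.2, so the infant can be held, restarted and counted on recurrence. An investigator may also hold and restart while relatedness is still being judged.

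**Step 3. Consistency with the rest of the protocol.** Of the four triggers, 1 requires re-challenge and 3 do not. The allergy and liver triggers rest on attribution to study drug. The Probable category needs a response on withdrawal only. The hypoglycemia trigger therefore asks for more evidence than the protocol's own highest causality category.

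**Step 4. Other routes to the DSMB for a case in the first row.**
- The opening of Section 5.4 says that all safety concerns which could lead to study termination are to be referred to the DSMB. This is mandatory, although someone must judge what qualifies.
- The medical monitor takes part in evaluating each Section 5.2 stop and is also the person who refers events to the chair.
- "Any SAE that is deemed potentially related to study medication, or of particular concern by the Medical Monitor" goes to the chair within 15 days, with no two-case minimum. Table 2 describes Grade 3 as severe or medically significant, with hospital admission or a longer stay indicated. Section 7.2 makes admission, a longer stay or an important medical event a ground for seriousness. A persistent Grade 3+ case unresponsive at 72 hours would nearly always be an SAE.
- Under Collective Events, AE rates are compared unblinded about every 4 months.

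Section 5.4 has the DSMB consider whether events, "both serious and related non-serious events, are occurring more frequently in the active arms", while the 15-day route covers SAEs only. By the previous bullets, few cases can fall into that gap.

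**Step 5. Whether the proposed wording drops anything.** Cross the four courses with two states: related and not explained by underlying disease, sepsis or PN weaning (R), or not (N). This gives 4 × 2 = 8 histories.
- Current text: recurrence in R or N, so 2 of 8.
- Proposed wording (see the fix): all 4 courses in R, plus stopped and recurs in N, so 4 + 2 = 6 of 8. Both histories counted now are kept. The stopped-in-N history can arise because Section 5.2 also allows stopping for other reasons.
- Relatedness required in every case: 4 of 8, losing 1 of the 2 counted now (recurrence in an infant judged N).

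These counts are unweighted. They show that the new wording contains the old one. They say nothing about how often cases are missed.

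**The case against.** The strongest reply is that re-challenge is a deliberate attribution filter. Hypoglycemia has many causes in these infants, the liver and autoimmune triggers carry filters of their own, and Sections 5.2 and 5.4 can be read as a sequence: hold, evaluate, re-challenge if relatedness is unclear, then stop. This stands as a reason to keep a filter, and to keep it tight. Counting every case deemed at least possibly related would be too loose, because the Possible category in Section 7.1.1 includes events that concurrent disease could explain. It does not justify making re-challenge the only filter, since an infant stopped because relatedness was clear then goes uncounted.

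The second reply is that the DSMB will hear of these cases anyway. That largely stands, for the reasons in Step 4. The DSMB charter (Section 10.3), which is not among the documents, may also deal with the matter.

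Three stronger readings are tempting and are not supported. A reader might infer that Section 5.2 makes the trigger impossible to meet; Step 2 shows otherwise. A reader might infer that drug-related hypoglycemia would escape the DSMB; the mandatory referral, the 15-day SAE route and the periodic unblinded review say otherwise. A reader might infer that the protocol tells sites to re-expose an infant who has been harmed; Section 5.4 only defines which cases count and directs no one to re-challenge.

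**Conclusion.** The point holds as a minor defect of wording. The hypoglycemia count omits infants stopped under Section 5.2 for a related Grade 3–4 episode, who are the cases most suspected of being drug-related, and it is the only one of the four triggers built this way. The effect is confined to the completeness of one count that prompts review by the DSMB chair. There is no loss of DSMB oversight and no effect on the efficacy conclusions.

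The conclusion rests on reading the conditions as joint, as written, and on a Section 5.2 stop being permanent, since no restart is described. A probability of missing the two-case threshold would need both an event rate and the share of infants stopped at the first episode. The documents give neither, so none is claimed.

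**What to change.** In the Section 5.4 bullet, keep the two-case minimum, the persistence and grade conditions and the 72-hour condition. Replace the recurrence condition with:

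*and either (a) is considered related to study medication and not attributable to underlying disease, sepsis or PN weaning, or leads to discontinuation of study medication under 5.2 for that event; or (b) recurs after a temporary stop and re-challenge.*

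Recurrence on re-challenge then suffices but is not required, and the exclusions in (a) keep a filter comparable to that of the liver trigger. If the DSMB charter repeats the trigger, make the same change there.

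The cost is one sentence, with no extra samples or visits. The downside is possibly a few more referrals to the DSMB chair, who still decides whether a full review is needed.

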**Collective Events:**

The Medical Monitor and DSMB will review aggregate safety data in an ongoing manner, at DSMB meetings which will be held approximately each 4 months throughout the trial. The Medical Monitor will remain blinded to treatment assignment for cumulative data at all times, but may refer any safety concerns based on review of safety data to the DSMB for further evaluation. The DSMB will receive unblinded safety data summaries from an independent statistician that is assigned to prepare the unblended study reports for all subjects at each DSMB meeting. Reviews of cumulative safety data will be conducted every four (4) months during the trial conduct during scheduled DSMB meetings. The DSMB statistician will compare the event rates for AEs between the groups and the probability that the groups differ in the frequency of events. If there are differences in Grade 3 or higher adverse events that differ materially between active and control and that may be attributable to study medication based on the mechanism of action of the drug, the DSMB has the option to recommend that the Sponsor stop the study, or modify the protocol for safety reasons.

The study may also be prematurely terminated for administrative reasons, ethical considerations, at the request of local regulatory agencies, or for any other reason the Sponsor deems appropriate.

**5.5. DEVIATION FROM STUDY PROTOCOL**

The investigator shall not deviate from the study protocol without first obtaining written approval from the Sponsor, or its official designee, and from the local IRB/IEC according to local regulations.

In the event of medical emergencies, the investigator shall use appropriate medical judgment and will remove the subject from any immediate hazard. Then, within 24 hours for related SAEs and within 48 hours for unrelated SAEs, the investigator shall notify the Sponsor or its official designee and, if applicable, the local IRB/IEC of the type of emergency and course of action taken.

Any other changes to or deviations from the protocol will be made as an amendment to the protocol and must be approved by the Sponsor or its official designee and the local IRB/IEC before they can be implemented. Accordingly, the Sponsor will not assume responsibility or liability for any unauthorized deviation from or change to the protocol.

**6. INVESTIGATIONAL PRODUCT SPECIFICATIONS**

NTRA-9620 drug product is manufactured in accordance with current Good Manufacturing Practices (cGMPs).

## **6.1. FORMULATION, PACKAGING, AND LABELING OF NTRA-9620**

NTRA-9620 (4 IU/g, 8 IU/g), which contains recombinant human insulin as the active ingredient, is intended for oral administration to infants with SBS.

NTRA-9620 consists of maltodextrin, 0.45% sodium chloride, and human insulin (rDNA origin).

To maintain double blinding, for the lower dose (4 IU/kg/day) stick packs will have powder concentration of 4 IU/g while for the high dose (8 IU/kg/day) stick packs will have powder concentration of 8 IU/g.

NTRA-9620 and matching placebo will be supplied in 1gram stick packs as a powder for reconstitution for oral administration. The stick packs will be provided in box cartons.

NTRA-9620 or Placebo will be labeled with at least the minimum information listed below:

NTRA-9620 or Placebo

Equivalent to 4 IU Insulin or 8 IU Insulin or Placebo in 1 stick pack for oral solution

Dose according to study protocol instructions

Store at room temperature (15-25°C/59-77°F)

Caution: New Drug – Limited for Clinical Trial Use Only

## **6.2. STORAGE AND STABILITY OF NTRA-9620**

The NTRA-9620 packets will be stored at room temperature (15-25°C ± 2°C/59-77°F ± 4°F). Storage space will be separate, designated, and adequately labeled as containing investigational product.

A stability program of NTRA-9620 is ongoing. The Sponsor will manage site inventory according to accumulating stability data and through the IVRS system.

### **6.2.1. Dosage**

NTRA-9620 (oral insulin) and matching placebo will be provided in stick packs of one gram for reconstitution.

### **6.2.2. Administration and Instructions for Use**

Each individual stick pack must be kept and handled at room temperature prior to reconstitution.

Subjects will receive SOC parenteral nutrition and enteral feedings containing either dose of NTRA-9620 or matching placebo. NTRA-9620 or matching placebo will be dosed to target an insulin dose of 8 IU/kg/day or 4 IU/kg/day for 24 weeks. NTRA-9620 and matching placebo can be reconstituted in normal (0.9%) or half normal (0.45%) saline (NaCl) and can be administered concomitantly with SOC infant formula, donor breast milk or own mother's milk used for enteral

feeds. During hospitalization, assigned treatment will be dosed 4 times a day as bolus administration spaced as equally over 24 hours as possible (ideally at every six (6) hours, but no less than three (3) hours between any two doses). In home care, subjects will receive assigned treatment four times a day (ideally at every six (6) hours, but no less than three (3) hours between any two doses). Additional instructions will be provided in the Instruction for Use document.

The SOC with NTRA-9620 or matching placebo will be manually shaken before consumption.

- Group 1: NTRA-9620 will be administered 4 times a day each at a dose of 2 IU/kg (8 IU/kg/day)
- Group 2: NTRA-9620 will be administered 4 times a day each at a dose of 1 IU/kg (4 IU/kg/day)
- Group 3: Matching placebo will be administered 4 times a day

